**Use Dec31yyyy**

Case 3: Only Year(yyyy) of the dose end date is available and yyyy = the year of EOT date:

### Use EOT date

Case 4: Both Year(yyyy) and Month (mm) are available for dose end date, and yyyy = the year of EOT date and mm < the month of EOT date:

### Use last day of the Month (mm)

All other cases should be considered as a data issue and the statistician should contact the data manager of the study.

After imputation, compare the imputed date with start date of treatment, if the imputed date is < start date of treatment:

### Use the treatment start date

Patients with missing start dates are to be considered missing for all study treatment component related calculations and no imputation will be made. If start date is missing then end-date should not be imputed. AE, ConMeds and safety assessment date imputation

**Table 5-1      Imputation of start dates (AE, CM) and assessments (LB, EG, VS)**

Missing Element	Rule
day, month, and year	No imputation will be done for completely missing dates
day, month	If available year = year of study treatment start date then If stop date contains a full date and stop date is earlier than study treatment start date then set start date = 01JanYYYY Else set start date = study treatment start date. If available year > year of study treatment start date then 01JanYYYY If available year < year of study treatment start date then 01JulYYYY
Day	If available month and year = month and year of study treatment start date then If stop date contains a full date and stop date is earlier than study treatment start date then set start date= 01MONYYYY. Else set start date = study treatment start date. If available month and year > month and year of study treatment start date then 01MONYYYY If available month and year < month year of study treatment start date then 15MONYYYY

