## **Baseline**

For efficacy evaluations, the last non-missing assessment, including unscheduled assessments on or before the randomization date is taken as “baseline” value or “baseline” assessment. In the context of baseline definition, the efficacy evaluations also include PRO and performance status.

For safety evaluations, the last non-missing assessment, including unscheduled assessments on or before the date of start of study treatment is taken as “baseline” value or “baseline” assessment.

If patients have no value as defined above, the baseline result will be missing.

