## **Data analysis**

On analyzing laboratory, data from all sources (central and local laboratories (as applicable)) will be combined. The summaries will include all assessments available for the lab parameter collected no later than 30 days after the last study treatment administration date (see [Section 2.1.1](#)).

All the outputs will be provided overall and by treatment phase (induction, consolidation and continuation).

The following summaries will be produced for hematology and biochemistry laboratory data (by laboratory parameter and treatment):

- For laboratory tests where grades are defined by CTCAE version 5.0, shift tables using CTC grades to compare baseline to the worst on-treatment value
- For laboratory tests where grades are not defined by CTCAE version 5.0, shift tables using the low/normal/high/(low and high) classification to compare baseline to the worst on-treatment value.

The following listings will be produced for the laboratory data:

- Listings of all laboratory data, with CTC grades and classification relative to the laboratory normal range. Lab data collected during the post-treatment period will be flagged.
- Listing of all CTC grade 3 or 4 laboratory toxicities

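### A laboratory, ECG or vital-sign record whose partial date matches the month or year of treatment start is dated to treatment start, so a value taken after dosing can become the safety baseline

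*SAP*

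**What the plan says.** SAP Table 5-1 governs incomplete start dates for adverse events and concomitant medications and, by its title, incomplete dates of laboratory (LB), ECG (EG) and vital-sign (VS) assessments.

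- Day and month missing: the relevant branch opens "If available year = year of study treatment start date then".
- Day missing: the relevant branch opens "If available month and year = month and year of study treatment start date then".
- Both branches have one exception, "If stop date contains a full date and stop date is earlier than study treatment start date". Otherwise: "Else set start date = study treatment start date".
- A later month goes elsewhere: "If available month and year > month and year of study treatment start date then 01MONYYYY". An earlier month goes to the 15th, a later year to 1 January and an earlier year to 1 July.

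SAP 2.1.1, under Baseline, states: "For safety evaluations, the last non-missing assessment, including unscheduled assessments on or before the date of start of study treatment is taken as" the baseline. Start of study treatment, in the same section, is the first non-zero dose of any component, which is chemotherapy Day 1.

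The safety outputs that use this baseline include, in SAP 2.8.3, "shift tables using CTC grades to compare baseline to the worst on-treatment value"; in SAP 2.8.4.1, QTcF increases of more than 30 and more than 60 ms; and, in SAP Table 2-5, changes in blood pressure, pulse and weight.

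**The concern.** Moving an unknown date to Day 1 is cautious for an adverse event, because the event then counts as treatment-emergent. For an assessment the same move works differently: it makes a value of unknown timing eligible as baseline. If the value was really taken under chemotherapy or study drug, every change computed for that patient and parameter is measured from an on-treatment value.

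The safety comparison is small. With 62 patients randomized 1:1 there are about 31 per arm, so one patient moving between categories shifts a percentage by about 1/31 = 3 points.

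The SAP takes more care in comparable places. It keeps completely imputed dates out of the last contact date (SAP 2.1.1), restricts the biomarker baseline to the pre-dose screening sample (SAP 2.12.4), and dates incomplete efficacy assessments from related investigations or neighbouring assessments (SAP 5.1.1.1). None of these safeguards is written for the safety baseline.

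**Working it through.** The plan states no figure on this point, so the check is to follow the rule and then see how far it reaches.

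**Step 1. Does the stop-date exception ever apply?** It needs a full stop date before treatment start. Laboratory, ECG and vital-sign records carry a single date, and the companion end-date table (SAP Table 5-2) covers only adverse events and concomitant medications. I therefore take it that the exception cannot apply to assessments.

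**Step 2. Run each branch**, with treatment start on 5 March 2019 as an illustration.

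| Known part of the date | Imputed date | Eligible as baseline? |
|---|---|---|
| March 2019 | 5 March 2019 | yes, as the latest possible date |
| 2019 only | 5 March 2019 | yes, as the latest possible date |
| April 2019 | 1 April 2019 | no |
| February 2019 | 15 February 2019 | yes, but truly pre-treatment |
| 2020 only | 1 January 2020 | no |

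Only the first two rows can turn a post-dose value into baseline. In those rows the record outranks any fully dated screening value. If a real Day 1 record exists the two tie, and the SAP gives no tie rule. Protocol Table 7-4 schedules no Day 1 ECG, so a mis-dated ECG would meet no scheduled competitor and would displace screening directly.

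**Step 3. How often is a post-dose record caught, given that its date is partial?** Take all 365 start dates in 2019 as equally likely.

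- Day missing: a record truly from Day k stays in the start month unless treatment began in the last k − 1 days of a month. The share caught is 1 − 12(k − 1)/365. Day 8: 1 − 84/365 = 77%. Day 11: 1 − 120/365 = 67%. Day 15: 1 − 168/365 = 54%. Day 21: 1 − 240/365 = 34%. Day 28: 1 − 324/365 = 11%.
- Day and month missing: the share caught is 1 − (k − 1)/365. Day 8: 98%. Day 21: 345/365 = 95%. Day 28: 338/365 = 93%.

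These shares are conditional on the date being partial. The documents do not say how often that happens.

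**Step 4. What it does to one patient.** The QTcF values here are invented to show both directions.

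- *Masking.* Treatment start 5 March; screening 430 ms on 3 March; true Day 8 value 495 ms with the day missing; Day 11 value 498 ms. As written, the 495 ms record is dated 5 March and becomes baseline, so the largest increase is 498 − 495 = 3 ms. With the screening baseline it is 498 − 430 = 68 ms, in the category above 60 ms.
- *Exaggeration.* Screening 468 ms; true Day 11 value 405 ms with the day missing; later value 500 ms. As written, the increase is 500 − 405 = 95 ms. With the screening baseline it is 500 − 468 = 32 ms.

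**The case against.** The best case against is that this will rarely happen and that little depends on it.

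- **ECGs are poor candidates.** Protocol 7.1 requires them on the specified day, Protocol 7.2.2.7.1 has central results transferred automatically, and Table 7-4 labels the screening tracing as the pre-dose baseline. This stands as to likelihood. The label is not carried into SAP 2.1.1, however, and that is the rule a programmer will follow.
- **Data cleaning should catch most partial dates.** Automatic checks and queries are described in Protocol 9.3 and 9.4. This also stands, and it is why the number is probably small.
- **Many outputs do not use baseline.** Adverse-event tables, the listing of grade 3 or 4 laboratory toxicities and the full laboratory listings keep the raw values. This largely stands. Two outputs that look absolute are partly exposed: the liver table in SAP 2.8.3 counts worst post-baseline values, so a record taken as baseline drops out; and the QTcF categories in SAP 2.8.4.1 count new values, which a value already present at baseline arguably is not.
- **A record that truly was pre-dose may do no harm** when dated to treatment start. This stands.

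A reader might also infer that about 80% of day-missing records in the start month are post-dose, by counting the 12 induction visits from Day 2 to Day 28. In a 30-day month these average 7.53 visits, against one Day 1 visit and 0.90 to 0.97 screening visits. That count does not fit ECGs, which in induction are scheduled only on Days 8, 11 and 21: 23/30 + 20/30 + 10/30 = 1.77 visits against the same 0.90 to 0.97, or about 65%. For laboratory tests and vital signs I could not confirm an assessment at all 12 visits, and Protocol 7.1.4 speaks of two assessments a week. Either figure also assumes that every visit is equally likely to lose its day, and each is a share of a set that may be empty.

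**Conclusion.** The interaction is real as the SAP is written. A record with the day missing in the month of treatment start, or with only the year known in the start year, becomes eligible as safety baseline whether or not it was taken before dosing, and nothing in the SAP prevents it.

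A reader might infer that any partly dated result is pulled to baseline and that toxicity is thereby hidden. The documents do not support that. The other branches of Table 5-1 create no such problem, and the distortion can run either way.

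The size cannot be stated, because the number of such records is not given; it is probably small. The effect is confined to baseline-dependent safety outputs for the affected patient and parameter. EFS, the other efficacy endpoints and the success criterion are not touched. The conclusion rests on assessments having no stop date and on there being no further baseline rule in programming specifications outside these documents.

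**What to change.** Make two changes to the SAP.

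1. In SAP 2.1.1, under Baseline, add that a laboratory, ECG or vital-sign record with an imputed date may not serve as safety baseline unless its nominal visit is screening or other recorded information shows it was taken before the first dose.
2. In Table 5-1, for LB, EG and VS only, and only in the branch where the known month and year (or the year alone) match treatment start, derive the date from the nominal visit instead of the treatment start date. Protocol Table 7-1 assigns visit numbers, so this is feasible.

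The other branches can stay. Removing these data types from Table 5-1 altogether would be wider than the problem requires.

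The cost is a small change to one date derivation and no new data. A few patients may be left with a missing baseline for a parameter. A count of the affected records would show whether any reported result changes.

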**Table 5-2      Imputation of end dates (AE, CM)**

Missing Element	Rule (*=last treatment date plus 30 days not > (death date, cut-off date, withdrawal of consent date))
day, month, and year	Completely missing end dates (incl. ongoing events) will be imputed by the end date of the on-treatment period*
day, month	If partial end date contains year only, set end date = earliest of 31DecYYYY or end date of the on-treatment period *

Missing Element	Rule (*=last treatment date plus 30 days not > (death date, cut-off date, withdrawal of consent date))
day	If partial end date contains month and year, set end date = earliest of last day of the month or end date of the on-treatment period*

Any AEs and ConMeds with partial/missing dates will be displayed as such in the data listings.

Any AEs and ConMeds which are continuing as per data cut-off will be shown as 'ongoing' rather than the end date provided.

#### 5.1.1.1 Other imputations

##### **Incomplete date of initial diagnosis of cancer and date of most recent recurrence**

Missing day is defaulted to the 15th of the month and missing month and day is defaulted to 01-Jan.

##### **Incomplete assessment dates for efficacy assessment**

If the date of assessment collected in the eCRF IWG Response page is incomplete but other relevant investigation dates (e.g., bone marrow aspirate, peripheral blood counts) are available, assessment date is calculated as the latest of all investigation dates (e.g., bone marrow aspirate, peripheral blood counts) if the overall response at that assessment is CR/CRp/PR (see [\[study protocol Section 7.2.1\]](#)). Otherwise – if overall response is treatment failure/relapse – the assessment date is calculated as the earliest date of all investigation dates at that evaluation. If all measurement dates have no day recorded, the 1st of the month is used. If the month is not completed, for any of the investigations, the respective assessment will be considered to be at the date which is exactly between previous and following assessment. If a previous and following assessment is not available, this assessment will not be used for any calculation.

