7.1.8 Follow up for efficacy evaluations

Patients who discontinue study treatment for reasons other than death, disease persistence or relapse (designated as Progressive Disease in the eCRF) should continue to have bone marrow assessments as scheduled in the protocol until relapse, as outlined in [Section 7.1](#).

After the Safety Follow-up visit, patients will enter the post-treatment follow-up phase.

During this phase, the following data will be collected:

- Antineoplastic therapy/transplantation after discontinuation of treatment: every 2 months during first 2 years then every 3 months for years 3 and 4, and then yearly.

The following assessments will be performed:

- Vital signs, blood samples for hematology [REDACTED] every 2 months for years 1 and 2, every 3 months for years 3 and 4 and then yearly

[REDACTED]

[REDACTED]

[REDACTED]

[REDACTED]

- Questionnaires (EORTC QLQ-C30 / PGIC): Every 4 months during the first year.

Patients will be followed in post-treatment follow up until relapse or end of study, whichever occurs first.

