### **1.1.2.2 Treatment phase**

#### **Induction therapy**

All screened patients will start induction therapy with chemotherapy (daunorubicin and cytarabine) from Day 1 to Day 7, while the FLT3 mutation is being determined.

An Interactive Response Technology (IRT) system will be used to randomize patients to the study treatment groups and the patient eligibility checklist will be embedded into the IRT randomization process.

Only randomized patients (with FLT3 mutation) will receive midostaurin/placebo, orally twice a day, on days 8 to 21.

Patients who achieve CR already with induction cycle 1 will go directly to consolidation therapy without a second cycle of induction therapy. Patients who do not achieve CR with one cycle of induction will receive a second induction cycle with same treatment than in cycle 1.

Patients not achieving CR after induction 2 will discontinue study treatment and will be followed in safety follow-up and survival follow-up.

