### Randomized part (Part 2)

The primary efficacy variable for the part 2 is event-free survival (EFS), defined as the time from the date of randomization until an EFS event is observed. An EFS event is defined as a failure to obtain a CR within induction 2, relapse after CR, or death due to any cause, whichever occurs first. Patients who do not complete first course of therapy without documented post-baseline CR should be considered a treatment failure. Clinical response (CR, CRp, PR and treatment failure, and relapse after CR) will be assessed via local review according to criteria defined in [Section 2.7.1](#). Relevant assessment date collected in the eCRF International Working Group (IWG) Response page will be used for the date of clinical response. For patients with treatment failure, the EFS will be documented as event at day 1 (refer to [Table 2-4](#)).

The final analysis for the part 2 will be based on FAS and will include all data observed up to the LPLV. If a patient has not observed EFS event at the LPLV, EFS will be censored at the date of the last adequate clinical assessment before the LPLV.

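### A known relapse whose assessment date lacks a month is discarded, because the SAP's date rule needs a later assessment and disease assessment normally stops at relapse

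*SAP*

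**What the plan says.** SAP 5.1.1.1 (Incomplete assessment dates for efficacy assessment) applies only when the assessment date on the IWG Response page is incomplete. It then works in steps.

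- With usable investigation dates, remissions take the latest date. For failures, "if overall response is treatment failure/relapse – the assessment date is calculated as the earliest date of all investigation dates at that evaluation".
- If no measurement has a day, the 1st of the month is used.
- A missing month in even one investigation triggers a midpoint rule, under which "the respective assessment will be considered to be at the date which is exactly between previous and following assessment".
- Where those neighbours do not exist, the SAP gives this consequence: "If a previous and following assessment is not available, this assessment will not be used for any calculation".

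The last two steps make no distinction by response.

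On follow-up, Protocol 7.1.8 states: "Patients will be followed in post-treatment follow up until relapse or end of study, whichever occurs first". Protocol 4.1.2.3 and SAP 1.1.2.3 agree that relapse moves the patient to survival follow-up. On induction failure, SAP 1.1.2.2 states: "Patients not achieving CR after induction 2 will discontinue study treatment and will be followed in safety follow-up and survival follow-up". SAP 2.5.1 fixes the date of that event: "For patients with treatment failure, the EFS will be documented as event at day 1".

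**The concern.** The midpoint rule needs an assessment on each side. A relapse is normally the last disease assessment, so it cannot have a midpoint and falls under the discard sentence. The event is known to have happened and only its date is imprecise, yet the patient is analysed as event-free and censored at the last remission assessment. That touches the primary endpoint and CIR.

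The rule also sits oddly with the rest of the SAP. The same section defaults the date of most recent recurrence to 01-Jan when month and day are missing, and Table 5-1 imputes start dates of adverse events and medications when day and month are missing. The protocol has the study unblinded after the primary analysis, so an unplanned decision on a single partial relapse date at the final analysis would be made with treatment known and would be open to challenge.

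**Working it through.** **1. Applying the rule to example sequences.** One assessment at a time is given an incomplete IWG Response date and a missing investigation month. It is kept only if an assessment exists before and after it.

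| Sequence | Kept | Dropped |
|---|---|---|
| Screening, CR, CR, CR, relapse | each CR | relapse |
| Screening, no CR, treatment failure | no CR | treatment-failure assessment |
| Screening, CR, CR, CR (still in remission) | first two CRs | last CR |

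If screening does not count as a previous assessment, the first post-baseline assessment is dropped as well. Reading the discard sentence as applying only when neither neighbour exists does not rescue the relapse: it would then have a previous assessment, no following one, and no rule for its date.

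**2. What happens to the patient.**

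- EFS (SAP Table 2-4): with the relapse gone, the patient is censored at the last adequate assessment. A later death is an EFS event if no more than one assessment was missed. After two or more it is censored.
- CIR (SAP 2.7.1): the patient is censored at the last adequate assessment unless death due to AML follows. That death counts, but later than the relapse.
- Treatment failure: EFS is dated at randomization + 1 and the event is the absence of a CR within induction 2, so no assessment date is needed. It is not a CIR event. One loose end remains. SAP 2.5.3 censors a patient with no post-baseline assessment only if still on treatment; Table 2-4 does so without that condition.

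**3. Size if loss is balanced between arms.** Inputs: HR 0.728 (Protocol Table 14-1), and 36 and 33 events with stated probabilities of success of 84.1% and 82.7% (SAP 3.1). With 1:1 allocation,

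P(estimated HR < 1) = Φ(√(d/4) × |ln HR|), |ln 0.728| = 0.317.

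- d = 36: Φ(3.000 × 0.317) = 83.0% (plan: 84.1%)
- d = 33: Φ(2.872 × 0.317) = 81.9% (plan: 82.7%)

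Both come within about one point of the plan's figures, which were obtained by resampling Study A2301. Losing events from 33:

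- 1 lost: 81.5%
- 2 lost: 81.2%
- 3 lost: 80.8%

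That is about 0.4 points per event.

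**4. How many relapses could be affected.** In Table 14-1, relapses were 98 + 102 = 200 of 521 events. So 33 events contain about 33 × 200/521 = 12.7 relapses. The share with both date faults is not in the documents. At an assumed 1%, 5% or 10%, the expected loss is 0.13, 0.63 or 1.27 relapses.

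**5. Size if the loss falls in one arm.** A simulation of 3000 trials was used: 31 patients per arm, treatment-failure rates of 34.7% and 42.0% from Table 14-1, about 36 events. Exponential relapse or death afterwards and 12 to 24 months of follow-up plus dropout are assumptions. Censoring one randomly chosen relapse multiplied the HR on average by 0.949 (midostaurin) or 1.048 (placebo).

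A crude check agrees. Splitting 36 events as in Study A2301 gives 36 × 244/521 = 16.9 and 36 × 277/521 = 19.1. Removing one event changes the HR by about 15.9/16.9 = 0.94 or 19.1/18.1 = 1.06.

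**The case against.** The strongest reply is that the rule will seldom fire. Two faults must coincide at one assessment: an incomplete date on the IWG Response page, and a missing month for an investigation. A complete response-page date settles the matter whatever else is missing. The protocol also provides for automatic data checks and queries on missing values (9.3, 9.4). This stands: the affected number may be zero.

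Three stronger readings are tempting, and the documents do not support them.

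- **Treatment failures are deleted too.** The assessment record may be dropped, but the event is defined by absence of CR and dated without it. A patient who fails induction 2 would normally also have a marrow from induction 1, and has discontinued study treatment, so the text of SAP 2.5.3 would not censor at randomization. Only the wording of Table 2-4 leaves doubt.
- **The rule deletes events and keeps remissions.** It is blind to response. The last CR of a patient still in remission is dropped as well, which moves the censoring date earlier.
- **The rule threatens the success claim.** SAP 2.5.2 notes that success was judged at the interim and/or primary analysis, not here. The documents do not show whether the plan for the primary analysis used the same rule.

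It is also fair to say that a 5% shift is small beside the sampling error: at 33 events the 95% interval runs from the estimate divided to multiplied by about exp(1.96 × √(4/33)) = 1.98. Nothing suggests that the loss would favour one arm. None of this answers the relapse case itself, where the SAP prescribes discarding a known event.

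**Conclusion.** The concern holds for relapse. When the IWG Response date is incomplete and an investigation month is missing, SAP 5.1.1.1 removes a documented relapse and turns the patient into a censored observation. EFS is then biased upward and relapse incidence downward. The effect on the HR could go either way, depending on the arm.

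The size rests on an unknown frequency. At assumed rates of 1% to 10%, between 0.13 and 1.27 relapses would be lost among 33 events. The cost is about 0.4 percentage points of P(HR < 1) per event if balanced, or an HR shift of about 5% for one event in one arm, given the simulation's assumptions. It bears on the final-analysis estimates, not on the success decision. For treatment failure, the only need is to remove an ambiguity. Severity: minor.

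**What to change.** Replace the last two steps of the date rule in SAP 5.1.1.1 for relapse, and add two statements.

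1. A documented relapse is always kept as an event and dated by the earliest complete investigation date. If no investigation has a month, use the midpoint between the last assessment without relapse and the first known upper limit: the end of the recorded year, the start of the next antineoplastic therapy, entry to survival follow-up, death, or last contact. The date is never earlier than the day after the last remission assessment. This bound should also cover the rule that uses the 1st of the month.
2. Treatment failure is an EFS event at randomization + 1 however complete the assessment date is. Align SAP 2.5.3 and Table 2-4 on patients with no post-baseline assessment.
3. List by arm every patient whose efficacy assessment date was imputed or could not be used.

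The cost is a short wording change and a few lines of derivation code. The downside is that a few relapse dates would be imputed.
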